### 2.3.2.5 OLE2 Period

After the implementation of Protocol Amendment #5.4 and 5.5 (with the addition of a 48-week Open-Label treatment period, ie, OLE2 Period), subjects from US and Canada sites will be invited to continue or reinstate their treatment as per the following OLE2 Groups:

- OLE2 Group A: Subjects in the treatment phase of the OLE Period at the time of Protocol Amendment #5.4 and 5.5 implementation will attend the Week 144 Visit and directly roll over to the OLE2 Period. These subjects will continue receiving bimekizumab 320mg Q8W for 40 additional weeks, starting from the first treatment visit of the OLE2 Period (ie, Week 144/OLE2 Baseline Visit; the Week 144 Visit will coincide with the Week 144/OLE2 Baseline Visit and data collected at this visit will be used as baseline data for the OLE2 Period)
- OLE2 Group B: Eligible subjects who have completed the Week 144 Visit and are in the SFU or have completed the SFU of the OLE Period at the time of Protocol Amendment #5.4 and 5.5 implementation, will be eligible to reinstate their treatment in the OLE2 Period after having undergone additional screening assessments during a 4-week OLE2 Screening Period
  - The first dose of the IMP will be administered at the OLE2 Baseline Visit and data collected at this visit will be used as baseline data for the OLE2 Period
  - Subjects in OLE2 Group B with an IGA score  $\geq 3$  at the OLE2 Baseline Visit will receive bimekizumab Q4W for the first 16 weeks, and then will switch to bimekizumab 320mg Q8W

- Subjects in OLE2 Group B with an IGA score <3 at the OLE2 Baseline Visit will receive bimekizumab Q8W from the OLE2 Baseline Visit.

Following completion or early withdrawal from the OLE2 Period, subjects will enter the SFU2 and will return for the SFU2 Visit 20 weeks after the last dose of IMP administration.

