### **2.3.3 Study duration per subject**

For each subject not entering the OLE2 treatment period, the study will last a maximum of up to 165 weeks, as follows:

- Screening Period: 2 to 5 weeks
- Double-blind Treatment Period: 48 weeks (final dose at Week 44)
- OLE Period: 96 weeks (final dose at Week 136 for subjects receiving bimekizumab 320mg Q8W and at Week 140 for subjects receiving bimekizumab 320mg Q4W)
- Safety Follow-Up Period: an SFU Visit is planned 20 weeks after the final dose of IMP during the OLE period (this SFU will not apply to subjects directly rolling over from the OLE to the OLE2 Period).

The OLE2 Period will include a 48-week treatment period with a final visit at OLE2 Week 48 and a SFU2 period of 20 weeks after the final dose of IMP administered in the OLE2 Period.

For the subjects in the OLE2 Period, maximum study duration will depend on the time between their participation in the OLE until Week 144 and the start of the OLE2 Period:

- 209 weeks for subjects still being treated in the OLE Period and who will directly roll over to the OLE2 Period at Week 144 visit
- 225 weeks for subjects who have completed Week 144 and the SFU; these subjects will have a 4-week Screening Period before reinitiating treatment in the OLE2 Period. Note: for these subjects, the study duration will not be continuous
- Between 209 and 225 weeks for subjects who have completed Week 144 and are ongoing in the SFU. For these subjects, the maximum study duration will depend upon when they stop the 20-week SFU period to enter the 4-week OLE2 Screening Period.

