## **3.6 Treatment assignment and treatment groups**

It is expected that subjects receive treatment as randomized and hence safety analyses will be based on the SS, as randomized. However, if after unblinding it is determined that subjects randomized to a treatment arm had never received such treatment, then for safety analysis, these subjects will be reallocated to the appropriate received treatment groups, unless otherwise specified.

If subjects randomized to secukinumab received bimekizumab at any time, then for safety analyses these subjects will be reallocated to the appropriate bimekizumab treatment group, unless otherwise specified. Subjects randomized to bimekizumab will only be reallocated to the secukinumab treatment group if they never received bimekizumab.

Efficacy analyses should be performed according to randomized treatment and not actual treatment received.

Randomized treatment groups are Bimekizumab 320mg Q4W and Secukinumab 300mg Q4W. Maintenance treatment groups are Bimekizumab 320mg Q4W, Bimekizumab 320mg Q8W, and Secukinumab 300mg Q4W.

Re-randomized (Open-Label extension) treatment groups are Bimekizumab 320mg Q4W and Bimekizumab 320mg Q8W. Unless otherwise specified, the OLE period will be summarized by treatment sequence comprising randomized treatment at Baseline and OLE period treatment at Week 48.

The following treatment sequences will be used to summarize efficacy data and specific safety data related to laboratory, ECG, PHQ-9, eC-SSRS, and vital signs assessments:

- Subjects receiving bimekizumab in the double-blind treatment period:
  - Initiating OLE on bimekizumab Q8W

- 
- Initiating OLE on bimekizumab Q4W
  - Subjects receiving secukinumab in the double-blind treatment period
    - Initiating OLE on bimekizumab Q8W
    - Initiating OLE on bimekizumab Q4W
  - All Subjects

Adverse event data (including for a subgroup of subjects who switched from Q4W to Q8W during OLE period) and study compliance data will be summarized in 2 treatment groups based on the dose most recently received prior to the date of the event or assessment

- Bimekizumab 320mg Q8W
- Bimekizumab 320mg Q4W
- Bimekizumab Total

In addition, the following key efficacy variables:

- PASI90 response
- PASI100 response
- IGA Clear or Almost Clear (with at least a 2-category improvement from Baseline)
- IGA Clear (with at least a 2-category improvement from Baseline)

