### 10.2.1 Data considerations

TEAEs are defined as those AEs that have a start date on or following the first dose of study treatment through the final dose of study treatment + 140 days (covering the 20-week SFU period). If it is not possible (due to partial dates) to determine whether or not an AE is treatment-emergent then it will be assumed to be a TEAE.

The rules for imputing partial start or stop dates are outlined in Section 4.2.1.7.

If the intensity of an adverse event is unknown, it is considered as severe. If the relationship to study drug is missing, it is considered as related.

AEs will be presented as “number of subjects (percentage of subjects) [number of events]”. In this style of output, “[number of events]” will include all cases of an AE including repeat occurrences in individual subjects, while “number of subjects” will count each subject only once.

Subject time at risk represents the time a subject is at risk for having an AE. The definitions for subject time at risk (in days) are outlined in Section 10.1. These definitions will be used for exposure-adjusted AE summaries.

Selected AE summaries will include the exposure adjusted incidence rate (EAIR) with associated 95% CI and the exposure adjusted event rate (EAER).

The EAIR is defined as the number of subjects (n) with a specific AE adjusted for the exposure and will be scaled to 100 patient-years:

$$EAIR = 100 \times n / \sum_{i=1}^N (T_{Exp(i)})$$

Where  $T_{Exp(i)}$  is the exposure time for the  $i^{th}$  subject and N is the number of subjects at risk.

If a subject has multiple events, the time of exposure is calculated to the first occurrence of the AE being considered. If a subject has no events, the total time at risk is used.

Exact Poisson 95% confidence intervals for incidence rates are calculated using the relationship between the Poisson and the Chi-square distribution (Ulm, 1990; Fay and Feuer, 1997):

$$LCL = \chi^2_{2n, \alpha/2} / 2$$

$$UCL = \chi^2_{2(n+1), 1-\alpha/2} / 2$$

where n is the number of subjects with a specific AE for the incidence rate of interest and is the basis for the number of the degrees of freedom for the chi-square quantile for the upper tail probability  $\chi^2$ .

The EAER will be the number of AEs including repeat occurrences in individual subjects divided by the total time at risk scaled to 100 patient-years and calculated using:

$$EAER = 100 \times N_{AE} / \sum_{i=1}^N (T_{Risk(i)})$$

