### 10.3 Clinical laboratory evaluations

If not specified otherwise, laboratory values, including markedly abnormal laboratory values will be presented descriptively by treatment group for the SS. Tables presenting markedly abnormal values and those based on CTCAE grade only include selected laboratory variables.

For tables where data are summarized by visit, unscheduled and repeat visits will not be summarized, but these data will be included in listings. For tables where multiple measurements over a period of time are considered (as in shift tables), unscheduled and repeat visits will be considered as long as they were collected in the period being summarized. All summaries will be presented in SI units and will be based on observed case values. In the case where laboratory values are below the lower limit of quantification, then these will be set to the midpoint between 0 and the lower limit of quantification for the purpose of summarizing the data. The following summaries are required:

- A summary of observed results and change from Baseline values in each laboratory variable by treatment group and visit
- A summary of the number and percentage of subjects experiencing markedly abnormal values at any time while on treatment (assessment on or following the first dose of study treatment through the final dose of study treatment + 140 days) by laboratory variable and treatment group. Two separate tables will show results for the initial treatment period (for the SS) and the Initial and Maintenance Treatment Period (for the MS). An additional table for the OLE period will be provided for the OLS by treatment the subjects were receiving at the time of the assessment of the abnormal value.
- A summary of the number and percentage of subjects with a given CTCAE grade (0, 1, 2, 3, or 4) based on minimum/maximum post-baseline value by laboratory variable and treatment group. Two separate tables will show results for the initial treatment period (for the SS) and the Initial and Maintenance Treatment Period (for the MS). An additional table for the OLE period will be provided for the OLS by treatment the subjects were receiving at the time of the assessment of the value with the given CTCAE grade.

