Markedly abnormal values are defined as those with a severity of Grade 3 and above based on the common terminology criteria for adverse events (CTCAE) criteria (U.S. Department of Health and Human Services 2010). Definitions of markedly abnormal values using the Grade 3 cut points are given in the tables below for age ranges of  $\geq 17$  years (Table 10–1 for markedly abnormal liver function test values, Table 10–2 for markedly abnormal biochemistry values and Table 10–3 for markedly abnormal hematology values). Tables summarizing markedly abnormal values should include a summary (counts and percentages) of markedly abnormal labs observed at any time while on treatment (ie, treatment-emergent markedly abnormal [TEMA]). For this summary, Baseline values and values observed more than 140 days after the last administration of study medication are not considered. The laboratory results classified as Grade 3 or Grade 4 will be summarized and listed separately.

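### The TEAE window was not split when OLE2 Group B was added, so adverse events recorded in the off-drug gap before the first OLE2 dose meet the TEAE definition but have no matching time at risk

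*SAP*

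**What the plan says.** Section 10.2.1 (Data considerations) gives one interval for treatment emergence: "on or following the first dose of study treatment through the final dose of study treatment + 140 days (covering the 20-week SFU period". Section 10.3 uses the same interval for markedly abnormal laboratory values: "assessment on or following the first dose of study treatment through the final dose of study treatment + 140 days". A later sentence in 10.3 sets aside Baseline values and adds that "values observed more than 140 days after the last administration of study medication are not considered".

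Section 2.3.2.5 opens OLE2 to Group B, which includes subjects who have already completed the SFU. They "will be eligible to reinstate their treatment in the OLE2 Period after having undergone additional screening assessments during a 4-week OLE2 Screening Period". Section 2.3.3 adds, for the SFU completers: "Note: for these subjects, the study duration will not be continuous". Section 2.3.2 defines the OLE2 Period as starting with the first study drug administration at or after its baseline visit, so OLE2 doses are study treatment.

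Time at risk is handled by period. Section 10.1.4 caps it in the OLE at the last OLE dose plus 140 days, or at the first OLE2 dose if that comes sooner. Section 10.1.6 starts the OLE2 count at the first OLE2 dose.

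For adverse events in the OLE, Section 3.6 assigns the treatment group "based on the dose most recently received prior to the date of the event or assessment".

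**The concern.** The 140-day extension is meant to cover the 20-week follow-up after dosing ends. That works while dosing is one continuous course. Group B has two courses with a break between them, and the definition refers only to the first and the final dose overall. Read as written, it therefore does not close at the end of the first course.

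Elsewhere the SAP does treat OLE2 as a new course: it has its own safety baseline (Section 3.2), its own relative day (3.9), its own follow-up period (2.3.2.6) and its own time at risk (10.1.6). The TEAE window was not brought into line.

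At stake is the match between numerator and denominator in the exposure-adjusted rates. An event can be flagged treatment-emergent when the subject has been off drug for longer than the plan's own 140-day limit and is contributing no time at risk. Re-screening is also a point at which untreated subjects are examined and asked about their health, so some events are likely to be recorded there.

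**Working it through.** **Inputs from the SAP**
- Last OLE dose: Week 136 on Q8W (Section 2.3.3). First OLE dose: Week 48.
- SFU: 20 weeks, or 140 days, after the last OLE dose (2.3.2).
- OLE2 Screening for Group B: 4 weeks (2.3.2.5).
- Last OLE2 dose: OLE2 Week 40 (Table 7–3). SFU2: 20 weeks.
- Initial screening: up to 5 weeks.

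**Step 1. Reproduce the plan's own durations.**
- Group B after a completed SFU: 5 + 136 + 20 + 4 + 40 + 20 = 225 weeks, as stated in 2.3.3.
- Direct roll-over: 5 + 144 + 40 + 20 = 209 weeks, as stated.

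The timeline used here is therefore the plan's own.

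**Step 2. Locate the gap.**
- Last OLE dose plus 140 days: Week 136 + 20 = Week 156.
- Earliest OLE2 Baseline after a completed SFU: 156 + 4 = Week 160.
- Gap: 4 weeks = 28 days, all of it OLE2 Screening.

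**Step 3. Compare the window with the time at risk, counting from the first OLE dose.**
- Window as written: (160 + 40 + 20 − 48) × 7 = 1204 days.
- OLE time at risk: (136 − 48) × 7 + 140 = 756 days.
- OLE2 time at risk: 40 × 7 + 140 = 420 days.
- Sum at risk: 756 + 420 = 1176 days.
- Excess: 1204 − 1176 = 28 days, or 28/1176 = 2.4% of time at risk.

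With a last OLE dose at Week 140 the excess is again 28 days. Any off-study interval between the end of the SFU and the start of re-screening widens the gap day for day. The SAP does not give its length.

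**Step 4. Subjects who stop the SFU early (last dose Week 136).** Excess days = max(0, (screening start + 4 − 156) × 7).
- Screening starts by Week 152: 0 days.
- Week 154: 14 days.
- Week 156: 28 days.

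Only subjects who completed or nearly completed the SFU are affected.

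**Step 5. Order of magnitude, on an assumed rate.** The SAP gives no adverse event rate. At an assumed 100 to 250 events per 100 patient-years, 28 days correspond to 28/365.25 × 1.0 = 0.08 to 28/365.25 × 2.5 = 0.19 events per affected subject.

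**Step 6. Look for a rule that removes these events.** Section 10.2.2 has a carve-out for early discontinuers: events after day 112 are kept out of the Initial Treatment Period tables although they remain TEAEs. There is no counterpart for the OLE–OLE2 gap. The Bimekizumab Set tables leave out the OLE2 treatment period, but that period begins only at the first OLE2 dose, so the exclusion does not reach the gap.

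**The case against.** The strongest reply is that the safety tables are organised by period and the gap belongs to none. Under Section 2.3.2 the OLE ends at Week 144 or the PEOT visit, the SFU lasts 20 weeks after the last OLE dose, and OLE2 starts at its first dose. The OLE and OLE2 adverse event tables are separate, and no planned table pools them. The most-recent-dose rule in Section 3.6 sits among the OLE treatment groups, and OLE2 has its own grouping, so applying that rule to a gap event presupposes that the event belongs to the OLE. The reference to the SFU in the TEAE definition also suggests that 140 days after each course was intended.

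Much of this stands. A reader might infer that gap events are certain to enter the OLE Q8W counts, the rates and the registry disclosure; the text does not establish that. What does not follow is that the plan excludes them. They meet the stated definition, no rule drops them, and the only attribution rule that could reach them points to the last OLE dose. Whether they are counted is left to the programmer.

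Two further inferences fail:
- **Months of false TEAEs.** This would require adverse events to be collected between SFU completion and re-screening. The SAP does not show that; it describes participation as not continuous, and Section 6.3 provides for additional medical history at OLE2 Screening.
- **One screening laboratory set per subject counted as on-treatment.** The SAP does not list the OLE2 Screening tests. Section 10.3 plans no OLE2 table of markedly abnormal values, and its reference to the last administration can be read as the most recent dose.

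**Conclusion.** The point holds in a limited form. As written, Section 10.2.1 classifies as treatment-emergent any adverse event recorded more than 140 days after the last OLE dose and before the first OLE2 dose, in Group B subjects who completed or nearly completed the SFU before re-screening. Those days fall outside both time-at-risk intervals. The span is up to 28 days of OLE2 Screening per subject, plus any off-study time in which adverse events are collected.

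The effect on reported rates is conditional: if these events are assigned to the most recently received dose, they add to the numerator of the OLE exposure-adjusted rates with no matching exposure. The number of Group B subjects is not given, and only US and Canadian sites contribute. The total is probably small. The comparative double-blind efficacy and safety results are unaffected.

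The conclusion rests on reading the final dose of study treatment as the last dose in the study, OLE2 included, which is what the words say. It is worth correcting because a stated rule gives the wrong classification and the correction costs very little.

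**What to change.** In Section 10.2.1, define the TEAE window by treatment course:
- (a) from the first dose to the earlier of the last double-blind/OLE dose plus 140 days and the day before the first OLE2 dose;
- (b) from the first OLE2 dose to the last OLE2 dose plus 140 days.

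State that adverse events outside both windows are listed as off-treatment and not summarised as TEAEs. Use the same wording for the on-treatment laboratory window in Section 10.3, for consistency.

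The cost is about one sentence in each section and a change to the TEAE flag. A few events may move from tables to listings. The time-at-risk caps at last OLE dose plus 140 days and the OLE2 start at first OLE2 dose already follow these courses and need no change for this purpose.

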### **2.2.3 Safety variable(s)**

#### **2.2.3.1 Secondary safety variables**

The secondary safety variables include the following treatment emergent adverse events (TEAEs) and serious adverse events (SAEs).

- TEAEs adjusted by duration of subject exposure to IMP
- SAEs adjusted by duration of subject exposure to IMP

- TEAEs leading to withdrawal adjusted by duration of subject exposure to study treatment

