- Listing of COVID-19 Vaccine Interval TEAEs

The following summaries will be provided for the BKZ Set by treatment at the time of AE onset. These tables will include AEs from both the double-blind and Open-Label treatment period (excluding OLE2 treatment period). AEs that occurred while subjects received secukinumab will not be included.

- Incidence of TEAEs Overview
- Incidence of TEAEs per 100 Subject-Years
- Incidence of Serious TEAEs per 100 Subject-Years
- Incidence of TEAEs by decreasing frequency of PT

- Incidence of TEAEs per 100 subject years by SOC, HLT, and PT and by Time of Onset Relative to COVID-19 pandemic (prior to COVID-19 pandemic, during COVID-19 pandemic).

In addition, all summaries of TEAEs based on “100 subject years” will include EAIR (with 95% CI) and EAER.

The following summaries will be presented for subjects who switched from secukinumab to bimekizumab at Week 48. The analyses will assign AEs according to the AE onset date relative to last secukinumab dose and accounting for approximately 5 times half-life (Onset  $\leq$  140 days from last secukinumab dose or Onset  $>$  140 days from last secukinumab dose):

- Incidence of TEAEs Overview
- Incidence of TEAEs per 100 Subject-Years
- Incidence of Serious TEAEs per 100 Subject-Years

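### The exact Poisson 95% CI for the EAIR leaves out exposure and the per-100 scaling, so as written it bounds a count of subjects, not the rate

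*SAP*

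**What the plan says.** Section 10.2.1 defines the rate first: "The EAIR is defined as the number of subjects (n) with a specific AE adjusted for the exposure and will be scaled to 100 patient-years". The formula beside it divides 100n by the sum of the subjects' exposure times. Exposure stops at the first occurrence for a subject with the event and is the full time at risk otherwise. Selected AE summaries are to show "the exposure adjusted incidence rate (EAIR) with associated 95% CI", and the interval is introduced with "Exact Poisson 95% confidence intervals for incidence rates are calculated using the relationship between the Poisson and the Chi-square distribution".

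The printed limits are:

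- LCL = χ²(2n, α/2) / 2
- UCL = χ²(2(n+1), 1−α/2) / 2

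The explanatory sentence says that n is the number of subjects with the AE and that it is the basis for the "degrees of freedom for the chi-square quantile for the upper tail probability".

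Section 10.2.2 adds that every TEAE summary per 100 subject-years "will include EAIR (with 95% CI) and EAER". The first secondary safety variable in section 2.2.3.1 is "TEAEs adjusted by duration of subject exposure to IMP". SAEs and TEAEs leading to withdrawal are adjusted in the same way.

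**The concern.** The EAIR contains total exposure and a factor of 100, and its confidence limits contain neither. Limits that depend only on n cannot be limits for a rate, because the same n over different exposure must give a different rate and a different interval. No other current text in the SAP supplies the missing scaling.

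There is a second, smaller problem. The subscripts α/2 for the lower limit and 1−α/2 for the upper limit are right for lower-tail (cumulative) probabilities, but the sentence says upper tail.

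At stake are the intervals in every table per 100 subject-years: the Safety Set, Maintenance Set, Open-Label Set, Open-Label Set 2 and BKZ Set summaries in section 10.2.2, and the safety topics of interest in section 10.2.3. They are the stated measure of precision for the secondary safety variables.

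**Working it through.** The SAP gives no numerical EAIR interval to reproduce, so the printed formulas were evaluated directly.

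**Inputs from the SAP**
- α = 0.05, two-sided (section 10.2.1).
- 350 subjects per arm (section 2.4).
- Initial Treatment Period of 112 days (section 10.1.1); double-blind period of 48 weeks, that is 336 days (section 2.3.2).
- Days are converted to years by dividing by 365.25 (section 10.1).
- Bimekizumab subjects are re-randomized 1:2 to Q4W or Q8W at Week 16, and the Maintenance Period is 32 weeks, that is 224 days (sections 2.3.2.3 and 2.3.2).

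**Assumptions.** The event counts and the 50, 300 and 1000 patient-year (PY) exposures are illustrative. The other exposures are arm size times period length, with no dropout and no stopping at first event:
- 350 × 112 / 365.25 = 107.3 PY
- 350 × 336 / 365.25 = 322.0 PY

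**Step 1: what the printed limits bound.** For n = 10 with lower-tail quantiles, L = 4.80 and U = 18.39. The Poisson check gives P(X ≥ 10 | mean 4.80) = 0.025 and P(X ≤ 10 | mean 18.39) = 0.025. These are exact 95% limits for the expected count.

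**Step 2: limits for the rate.** With T the summed exposure in years, they are 100L/T and 100U/T. The printed limits are therefore T/100 times the correct ones: right only at T = 100, too high above it and too low below it.

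| T (PY) | n | EAIR | Printed CI | Correct CI | EAIR inside printed CI? |
|---|---|---|---|---|---|
| 50 | 10 | 20.00 | 4.80–18.39 | 9.59–36.78 | No |
| 107.3 | 10 | 9.32 | 4.80–18.39 | 4.47–17.14 | Yes |
| 300 | 10 | 3.33 | 4.80–18.39 | 1.60–6.13 | No |
| 322.0 | 1 | 0.31 | 0.03–5.57 | 0.01–1.73 | Yes |
| 322.0 | 5 | 1.55 | 1.62–11.67 | 0.50–3.62 | No |
| 322.0 | 10 | 3.11 | 4.80–18.39 | 1.49–5.71 | No |
| 322.0 | 20 | 6.21 | 12.22–30.89 | 3.79–9.59 | No |
| 322.0 | 100 | 31.06 | 81.36–121.63 | 25.27–37.78 | No |
| 1000 | 10 | 1.00 | 4.80–18.39 | 0.48–1.84 | No |

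**Step 3: when the printed interval contains its own estimate.** This requires 100n/U ≤ T ≤ 100n/L. The range is about 54 to 209 PY for n = 10, and about 65 to 164 PY for n = 20. The Initial Period, at about 107 PY per arm, falls inside both ranges, so the error would be hard to see there.

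**Step 4: coverage of the true rate at 322 PY.**

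| Expected count | Printed | Corrected |
|---|---|---|
| 5 | 44% | 98% |
| 10 | 22% | 97.5% |
| 20 | 4% | 95.7% |

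**Step 5: comparison between maintenance groups.** Take n = 10 in each group and 224 days of exposure:

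| Group | T (PY) | EAIR | Printed CI | Correct CI |
|---|---|---|---|---|
| Bimekizumab Q4W | (350/3) × 224/365.25 ≈ 72 | 14.0 | 4.80–18.39 | 6.7–25.7 |
| Bimekizumab Q8W | (700/3) × 224/365.25 ≈ 143 | 7.0 | 4.80–18.39 | 3.4–12.9 |
| Secukinumab | 350 × 224/365.25 ≈ 215 | 4.7 | 4.80–18.39 | 2.2–8.6 |

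Three rates that differ threefold get one interval, and it excludes the secukinumab rate.

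**Step 6: the tail wording.** With upper-tail quantiles and the printed subscripts, n = 10 gives LCL = 17.08 and UCL = 5.49. The interval is inverted.

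**The case against.** The best defence is that the section says what the interval is for and prints the EAIR denominator and scaling a few lines above. A statistician would probably read the two lines as limits for n, to be rescaled as n is. The intervals are descriptive: no multiplicity-controlled test uses them, and the bimekizumab-minus-secukinumab risk difference has its own complete formula. The Week 48 analysis is described as already done, so programs exist and may well divide by exposure. Over long periods a literal result would often exclude its own estimate and be noticed.

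Much of this stands as a limit on consequences. It does not make the formula right. The sponsor treats the formulas in this section as operative: Amendment 4 (section 13.4, Change #47) corrected one subscript in the risk-difference standard error and left these two lines alone. Self-detection also fails where exposure is near 100 PY, as in the Initial Period.

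Three further points are fair:

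- The tail wording is secondary, since an inverted interval could hardly pass unnoticed.
- The exposures are rough. Stopping at first event shrinks the denominator for common events, so the factor of about 3.2 over 48 weeks suits rare events best. Time at risk can also run to 140 days after the last dose for subjects who do not enter the OLE, so 322 PY is not a ceiling.
- AE tables go by treatment at onset, so 322 PY suits the secukinumab column or a bimekizumab total, not a single bimekizumab dose column.

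**Conclusion.** The concern holds. As written, section 10.2.1 gives confidence limits for a count and attaches them to a rate per 100 patient-years. They are wrong by a factor of summed exposure over 100: about 7% in the Initial Period (107.3/100), about 3.2-fold over 48 weeks for 350 subjects with a rare event (322.0/100), and more where longer open-label exposure accumulates. At 322 PY the printed interval misses its own point estimate at each of the counts of 5, 10, 20 and 100 evaluated.

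The factor itself needs no assumption. The sizes quoted rest on illustrative counts and full-period exposure. The upper-tail phrase is a separate wording error that contradicts the subscripts. EAIR point estimates, EAERs, risk differences and all efficacy tests are unaffected. The conclusion concerns the document as written; it does not show that any reported interval is wrong.

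**What to change.** Replace the two lines in section 10.2.1 with:

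- LCL = 100 × χ²(2n; α/2) / (2 × ΣT)
- UCL = 100 × χ²(2(n+1); 1−α/2) / (2 × ΣT)

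State that:

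- ΣT is the same exposure sum, in years, as in the EAIR denominator, including the stop at first occurrence.
- The second argument is a lower-tail (cumulative) probability, and delete the reference to the upper tail.
- LCL = 0 when n = 0. This is the usual convention, but the SAP does not give it.

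Then confirm that the programs for the Week 48, Week 96, Week 144 and final outputs already use this form. A table with exposure far from 100 patient-years is the useful check; an Initial Period table is not. If any program followed the printed lines, the affected intervals need to be re-run.

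The cost is two formula lines, one deleted phrase and a program check. No new data are needed.
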